### **7.3 Subject Population(s) for Analysis**

All subjects enrolled in the study received at least two doses of ipilimumab and SABR will be used for analysis of the primary endpoint.

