
Study Product, Dose, Route, Regimen
	
Ipilimumab will be administered on week 1 at a dose of 3 mg/kg. Subsequent cycles of ipilimumab will be given every three weeks (week 4, 7, & 10).
 
SABR will be delivered between the second and third doses of ipilimumab(week 5-6) using the following suggested schedules: 18 Gy x 3 to lung, 10 Gy x 5 to liver, 6 Gy x 6 to nodal stations, 12 Gy x 3 to adrenal, 18 Gy x 1 to bone, and 24 Gy x 1, 18 Gy x 1, 15 Gy x 1 to < 2.0 cm, 2.0-3.0 cm, and >3 cm brain metastases, respectively.
 
Duration of therapy: Patients will receive at least 12 weeks of therapy and will be observed for toxicity for 90 days after the last ipilimumab infusion. Patients will remain on study until evidence of progression or death.

Duration of administration
	
12 weeks

Reference therapy
	
NA

Statistical Methodology	
Overall, this study will require 32 evaluable patients. We estimate that we will accrue 1-2 patients per month. Thus, the minimum study duration will be 16 months and the maximum is 32 months.
 
Current literature and experience with maintenance therapy in this patient population shows that we can expect that this treatment regimen will not be considered promising in this patient population if at most 15% of patients are progression-free and alive at 6 months. For this agent to be considered promising in this patient population, we would expect an improvement in the 6-month PFS rate to at least 35% with this regimen in this patient population. Constraining the Type I and II error rates to 10% each, a 2-stage phase II Simon minimax study design will require 32 evaluable patients to test these hypotheses regarding the 6-month PFS rate with ipilimumab when given in combination with the stereotactic ablative radiation therapy in this patient population.

----------------------------	---

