SABR will be delivered between the second and third doses of ipilimumab (usually week 5-6 if no delays for ipilimumab toxicity) using the following suggested schedules: 18 Gy x 3 to peripheral lung, 10 Gy x 5 to central lung, 10 Gy x 5 to liver, 6 Gy x 5 to nodal stations, 12 Gy x 3 to adrenal, 24 Gy x 1 brain < 2 cm, 18 Gy x 1 brain 2-3 cm, and 15 Gy x 1 brain > 3 cm, 16-18 Gy x 1 to vertebral sites.

Duration of therapy: Patients will receive at least 12 weeks of therapy and will be observed for toxicity for 90 days after the last ipilimumab infusion. Patients will remain on study until evidence of progression by both mWHO and irRC or death. Patients in whom new lesions develop or baseline lesions grow will receive additional ipilimumab treatments to complete induction therapy.

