### **3.2 Primary Study Endpoints**

- Rate of progression-free survival of ipilimumab and SABR in patients with oligometastatic melanoma as measured from the time of study enrollment until the first documented date of disease progression by mWHO criteria

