## 7.0 STATISTICAL PLAN

### 7.1 Sample Size Determination

Overall, this study will require 32 evaluable patients. We estimate that we will accrue 1-2 patients per month; therefore, thus, the minimum study duration will be 16 months (2 accruals per month) and the maximum is 32 months (1 accrual per month for 32 patients).

Current literature and experience with ipilimumab in metastatic melanoma in this patient population shows that we can expect ipilimumab + SABR will not be considered promising in this patient population if at most 15% of patients are progression-free and alive at 6 months, because that is the expected 6 month PFS for ipilimumab alone. For this agent to be considered promising in this patient population, we would expect an improvement in the 6-month PFS rate to at least 35% with this regimen in this patient population. Constraining the Type I and II error rates to 10% each, the study design will require 32 evaluable patients to test these hypotheses regarding the 6-month PFS rate with ipilimumab when given in combination with the stereotactic ablative radiation therapy in this patient population. If we see at least 8 patients who have are alive and progression-free at 6 months after initiation of treatment out of the 32 evaluable patients, we will consider this sufficient evidence that this regimen has promising activity in this patient population. Otherwise, if 7 or fewer patients have are alive and progression-free at 6 months, we will consider this regimen to not be sufficiently active in this population of oligometastatic melanoma patients.

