### 7.2 Statistical methods

All evaluable patients will be included in calculating the 6-month PFS rate for the study along with corresponding 95% binomial confidence intervals (assuming the number of patients who are progression-free and alive at 6 months is binomially distributed). The numerator will be the number of patients at 6-months from enrollment who have either a complete response, a partial response, or stable disease (i.e. have not progressed) on re-staging imaging and who are alive. The denominator will be the number of patients on trial who received ipilimumab and SABR.

In addition, several secondary endpoints will be evaluated in these subjects:

- **Toxicity and Tolerability.** Frequency and severity of adverse events and tolerability of the regimen in each of the patient groups will be collected and summarized by descriptive statistics. As per NCI CTCAE v4.0, the term toxicity is defined as adverse events that are classified as either possibly, probably, or definitely related to study treatment. The maximum grade for each type of toxicity will be recorded for each patient, and frequency tables will be reviewed to determine toxicity patterns. In addition, we will review all adverse event data that

is graded as 3, 4, or 5 and classified as either “unrelated” or “unlikely to be related” to study treatment in the event of an actual relationship developing. The incidence of severe (grade 3+) adverse events or toxicities will be described. We will also assess tolerability of the regimens through assessing the number of patients who required dose modifications and/or dose delays. In addition, we will also capture the proportion of patients who go off treatment due to adverse reactions or even those who refuse further treatment for lesser toxicities that inhibit their willingness to continue participation on the trial. These tolerability measures will be assessed within each of the treatment arms and we will explore differences in these measures between the arms. All patients who have received at least one dose of any of the therapeutic agents in a treatment arm will be evaluable for toxicity and tolerability.

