- **Overall response.** All evaluable patients (i.e. eligible patients who have received at least two doses of ipilimumab and SABR) will be assessed in terms of their best response to therapy by both mWHO and irRC. Those who achieve a partial response (PR) or complete response (CR) will be considered responses and the overall response rate will be calculated as the number of PRs and CRs divided by the total number of evaluable patients. Best overall response rate will be reported taking into account all post-treatment imaging.
- **Overall survival and progression-free survival as continuous time-to-event outcomes.** All evaluable patients will be used for this analysis. Kaplan-Meier curves will be used to estimate overall and progression-free survival. Each of these variables is measured from the date of study registration to the date of event (i.e., death or disease progression). In the case of the overall survival endpoint the date of last follow-up is to be used if no event has occurred at their last evaluation. In the case of the progression-free survival endpoint the date of last tumor assessment is to be used if no event has occurred at their last evaluation.
- **Correlative markers:** Several correlative markers will be explored in this trial in relation to clinical outcomes of interest, and in particular in relation to the primary endpoint of 6-month PFS rate. Given the limited overall sample size as well as the relatively limited expected proportion of patients who are progression-free and alive at 6 months, these analyses will be largely exploratory and hypothesis-generating in nature. Markers will be summarized univariately in a quantitative manner and also summarized by clinical outcome group (e.g. prog-free and alive at 6 months vs. not). Graphical analyses will be largely used to assess potential patterns and relationships; e.g. side-by-side boxplots to assess differences in continuous marker levels between those with vs. without the clinical improvement. We may also explore changes in these markers in relation to baseline, with clinical outcome incorporated through use of different plotting characters. Overall, hypothesis testing will largely be avoided given the sample size limitations but we will still obtain important preliminary data that can inform future studies and help better understand the mechanisms of this treatment regimen in this patient population.

*Statistical and Data Analysis:*

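### The efficacy analyses keep only patients who reach two ipilimumab doses plus SABR, although time starts at enrollment: the 6-month PFS rate is biased upward if those lost earlier do worse, and replacing them can push type I error above 10%

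*Combined protocol and SAP*

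**What the plan says.** Section 7.3 states: "All subjects enrolled in the study received at least two doses of ipilimumab and SABR will be used for analysis of the primary endpoint". Section 7.2 gives a matching rule for the primary rate: "The denominator will be the number of patients on trial who received ipilimumab and SABR". For response, Section 7.2 defines evaluable patients as "eligible patients who have received at least two doses of ipilimumab and SABR", and it uses evaluable patients again for the OS and PFS Kaplan-Meier curves. Only toxicity and tolerability use everyone with at least one dose (Sections 6.8 and 7.2).

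SABR is given between the second and third infusions, usually week 5-6 (Section 3.1.2). Time starts earlier in every version the plan gives:

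- Section 3.2 defines the primary endpoint "as measured from the time of study enrollment until the first documented date of disease progression by mWHO criteria".
- Section 7.2 counts 6 months from enrollment for the rate, and uses registration for the curves.
- Section 7.1 counts 6 months from initiation of treatment.

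The 15% null is chosen "because that is the expected 6 month PFS for ipilimumab alone" (Section 7.1).

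Replacement is not addressed. Section 7.1 and the Study Summary require 32 evaluable patients. However, the Study Summary also lists 32 subjects, Section 7.4 speaks of a planned enrollment of 32, and Section 7.1 bases the longest accrual time on "1 accrual per month for 32 patients". The Study Summary says that "a 2-stage phase II Simon minimax study design will require 32 evaluable patients to test these hypotheses", while Section 7.1 gives only a single-stage rule: promising if at least 8 of 32 succeed.

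**The concern.** Membership of the analysis set depends on getting through the first five to six weeks, yet those weeks count towards the endpoint. Every analysed patient has by construction survived to SABR, so deaths before SABR can never enter the OS or PFS curves, and the early part of the OS curve can only be too high. The selected group is then judged against a null rate that has no such selection. No landmark at SABR and no efficacy analysis of all treated patients is planned.

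The protocol foresees such losses. Section 6.10 describes patients who miss SABR because of adverse events from the first two infusions and waives their re-staging. Section 3.1.4 leaves efficacy assessment after a toxicity stop to standard of care, and Section 3.1.2 asks treated patients only for a 12-week tumor assessment. The 6-month status of patients lost early may therefore be unknown, although deaths and reasons for stopping are recorded.

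At stake are the reported 6-month PFS rate with its interval and, if lost patients are replaced, the error rate of the trial's go/no-go decision.

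**Working it through.** **Inputs.** From Section 7.1: null 0.15, alternative 0.35, 32 evaluable patients, success at 8 or more, type I and II error 10% each. Assumed, because the documents do not give them: the share d of starters lost before SABR (5, 10, 15, 20%) and their 6-month success rate q. Two values of q are shown: 0 (all fail, an upper bound) and 0.075 (half the null rate).

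**The plan's own figure.** Exact binomial: P(X ≥ 8 | 32, 0.15) = 0.0958 and P(X ≥ 8 | 32, 0.35) = 0.9182. The rule meets its limits, with 0.4 points of slack on type I error.

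**Rate in the analysed set.** If the true rate among all starters is 0.15, the rate among those who reach SABR is p = (0.15 − d·q)/(1 − d). For d = 10% and q = 0 this is 0.15/0.90 = 0.1667. This shift applies whether or not patients are replaced.

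**Type I error if lost patients are replaced until 32 are evaluable.** P(X ≥ 8 | 32, p), taking patients started on the regimen as the target:

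| d | p, all fail | error, all fail | p, half null | error, half null |
|---|---|---|---|---|
| 5% | 15.8% | 12.0% | 15.4% | 10.8% |
| 10% | 16.7% | 15.2% | 15.8% | 12.2% |
| 15% | 17.6% | 19.1% | 16.3% | 13.9% |
| 20% | 18.8% | 24.0% | 16.9% | 16.0% |

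The error passes 10% once p exceeds 15.14%, that is at d of about 1% (all fail) or 2% (half null).

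**Two-stage reading.** The documents give no stage-1 values. An exact search at 15% versus 35% with 10%/10% finds no two-stage design below 32 patients. At 32, the design with the smallest expected size under the null stops at 2 or fewer of 17 and otherwise requires 8 of 32 (error 9.1%, power 90.5%). Taken as an illustration, with replacement its error becomes 11.4/14.4/18.2/22.9% (all fail) or 10.2/11.5/13.2/15.2% (half null) for the four values of d.

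**Enrollment fixed at 32, bar kept at 8.** A success among all 32 starters must now also reach SABR, which has probability 0.15 − d·q. The error is 9.6% at every d if all lost patients fail, and 8.5/7.6/6.7/5.8% at half null. It is not inflated, but the rate is still biased. Example: 32 start, 3 miss SABR and fail, 8 succeed. The plan reports 8/29 = 27.6% (Clopper-Pearson 95% interval 12.7 to 47.2) rather than 8/32 = 25.0% (11.5 to 43.4).

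No rule covers fewer than 32 evaluable. With 29, and 15% and 35% taken as their rates, a bar of 8 gives 5.9% error and 84.9% power; a bar of 7 gives 13.3% and 92.6%.

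**The case against.** The strongest reply is that neither the direction nor the size of the bias is established. The one route to missing SABR that Section 6.10 describes is toxicity, and Section 5.5 notes that responses have been maintained after ipilimumab was stopped. Early radiologic progression need not remove a patient (Section 3.1.2), and the first scheduled re-staging, before the third infusion, can come after SABR. If lost patients had a 20% success rate, the analysed rate at d = 10% would be (0.15 − 0.02)/0.90 = 14.4%, with type I error of about 8%. The nearest documented figure for d is in Section 1.5.2: ipilimumab was stopped for adverse reactions in 10% of patients over up to four doses, so 15 to 20% is unsupported for toxicity alone. Finally, Section 7.1 frames its test in 32 evaluable patients, and for that set the error is 9.6% whatever d is.

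Much of this stands as a limit. The bias is upward only if those lost do worse; the all-fail column is a bound; d is an assumption; and the inflated error needs replacement and takes all starters as the target. It does not remove the problem. The 10% figure does not cover deaths, deterioration or withdrawal before SABR. Deaths before SABR are failures that cannot be counted, and the null comes from patients not selected in this way. Small losses already matter because the rule has so little slack.

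**Conclusion.** The concern holds. The primary rate, response, OS and PFS are all computed in a set selected by events after time zero and, for the primary test, compared with an unselected null. That follows from the text and needs no assumption.

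The size does need assumptions. If excluded patients do worse than average, the 6-month PFS rate is too high: under a true 15%, by 0.4 to 0.8 points at 5% loss and 1.9 to 3.8 points at 20% loss (half null to all fail). If they are also replaced, type I error for patients started on the regimen exceeds the stated 10%, reaching 12.2 to 15.2% at 10% loss under the single-stage rule. If enrollment stops at 32 with the bar at 8, the error is not inflated and only the estimate is affected. If exclusion is unrelated to outcome, there is no bias. This should be fixed before the primary analysis.

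**What to change.** In Sections 7.2 and 7.3, make the primary denominator all enrolled patients who receive at least one ipilimumab dose, which is the safety set of Section 6.8, and count unknown 6-month status as not a success. Apply 8 of 32 to the first 32 such patients, and state in Section 7.1 that 15% and 35% refer to them. Type I error is then 9.6% and power 91.8%, and replacement is not needed. Use the same set for response, OS and PFS. Keep the two-doses-plus-SABR set as a labelled sensitivity analysis with its curves landmarked at SABR, and report how many patients were excluded before SABR and why.

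These texts also need to be reconciled:

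- 32 enrolled with 32 evaluable (Study Summary, Sections 7.1 and 7.4);
- the two-stage design of the Study Summary with the single-stage rule of Section 7.1;
- the three time origins (Sections 7.1 and 7.2);
- Section 4.5.2, which keeps withdrawn patients' data in the study analysis, with Section 7.3, at least to say which analyses are meant;
- the imaging text in Sections 3.1.2, 3.1.4 and 6.10, so that 6-month status is known for all treated patients.

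The cost is a short amendment and 6-month status for the patients who miss SABR. The reported rate may be lower, and so may power. If 35% holds only among patients who reach SABR and all others fail, the success probability is 0.35(1 − d), and the power of 8 of 32 is 88/84/78/71% at d = 5/10/15/20%. That is below the planned 90% and should be stated as a limit of the design.

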### **7.4 Interim Analysis- Safety**

Prior use of 3mg/kg ipilimumab alone has resulted in a 10-15% grade 3+ autoimmune related toxicity rate. If the addition of SABR to ipilimumab doubles the risk of grade 3+ autoimmune related toxicity, that would be unacceptable. Therefore, our null hypothesis will be that 70% or more of the patients will be severe immune related toxicity-free. We will conduct an interim analysis after the treatment of 18 patients to assess the null hypothesis versus the alternative hypothesis of 90% or more of the patients will be severe immune related toxicity-free. If at the interim analysis 14 or more patients are severe immune related toxicity-free then we will continue to enroll to the planned enrollment of 32 patients. If 5 or more patients have severe immune related toxicities we will consider this combination too toxic for further investigation.

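### The numeric toxicity rule is applied only after 18 patients are treated, although a fifth event settles it earlier; stopping accrual at that event leaves the decision unchanged

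*Combined protocol and SAP*

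**What the plan says.** Section 7.4 (Interim Analysis - Safety) starts from experience with ipilimumab 3 mg/kg alone, which "has resulted in a 10-15% grade 3+ autoimmune related toxicity rate". It then sets the standard for concern: "If the addition of SABR to ipilimumab doubles the risk of grade 3+ autoimmune related toxicity, that would be unacceptable". The hypotheses concern the proportion free of severe immune toxicity: "our null hypothesis will be that 70% or more of the patients will be severe immune related toxicity-free", against an "alternative hypothesis of 90% or more of the patients will be severe immune related toxicity-free".

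The rule is one look: "We will conduct an interim analysis after the treatment of 18 patients". There are two branches. "If at the interim analysis 14 or more patients are severe immune related toxicity-free then we will continue to enroll" to the planned 32. "If 5 or more patients have severe immune related toxicities we will consider this combination too toxic for further investigation". With 18 patients, 14 or more toxicity-free is the same as 4 or fewer events, so the branches are exact complements and describe the same look.

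Section 7.4 gives no error rate or stopping probability for this rule, no accrual hold at patient 18, and no numeric rule after it. The 10% error rates in section 7.1 belong to the 6-month PFS test.

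Two other places bear on the point. Under the Study Summary, patients "will be observed for toxicity for 90 days after the last ipilimumab infusion". Section 10.4 provides for investigator review at least monthly, a judgement by the principal investigator on whether to end the trial early, and DSMC review of serious adverse events. It sets no toxicity threshold.

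**The concern.** Events among the first 18 patients only accumulate. Once five have occurred, later patients cannot bring the count back to four, so the look can end only one way. A rule that waits for patient 18 therefore allows enrolment into a combination that already meets the plan's own criterion for too toxic. Those patients face a risk of severe immune toxicity and cannot alter the decision.

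A separate matter is how well the cut-off detects the toxicity that the plan calls unacceptable. Section 7.4 does not say, so an IRB or DSMC reading it cannot judge how much protection the number gives.

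Finally, treatment runs to week 10 and toxicity is followed for 90 days beyond that. The wording does not say whether patient 18 must be dosed, finish treatment or complete observation before the look. That choice determines how many more patients enrol in the meantime.

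**Working it through.** **Inputs.** Look at n = 18; stop at 5 or more events; planned total 32; background rate 10-15% (section 7.4). Doubling gives 20-30%. Accrual is 1-2 per month (section 7.1). Infusions are at weeks 1, 4, 7 and 10, with 90 days of observation after the last (Study Summary). The hypotheses are evaluated at their boundary values, 70% and 90% toxicity-free, which are 30% and 10% toxicity. Patients are taken as independent, with events known at once and in enrolment order.

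The plan prints no operating characteristic for this rule, so there is no figure to reproduce.

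**1. Stopping probability of the rule.** P(stop) = 1 - sum over x = 0 to 4 of C(18,x) p^x (1-p)^(18-x).

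At p = 0.30 the five terms are 0.0016, 0.0126, 0.0458, 0.1046 and 0.1681, which sum to 0.3327, so P(stop) = 0.667. At p = 0.20 they are 0.0180, 0.0811, 0.1723, 0.2297 and 0.2153, which sum to 0.7164, so P(stop) = 0.284.

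| True toxicity | P(stop) | P(continue) |
|---|---|---|
| 10% | 2.8% | 97.2% |
| 15% | 12.1% | 87.9% |
| 20% | 28.4% | 71.6% |
| 25% | 48.1% | 51.9% |
| 30% | 66.7% | 33.3% |

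At the plan's own 30% null the rule continues one time in three.

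**2. When the fifth event occurs.** P(fifth event at patient k) = C(k-1,4) p^5 (1-p)^(k-5). Summing k = 5 to 17 gives the chance that the outcome is fixed before patient 18. The conditional mean is the sum of k times this probability for k = 5 to 18, divided by P(stop). The last column averages over all trials, including those that never reach the boundary.

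| True toxicity | P(fifth event in first 17) | Mean patient number of fifth event, if boundary reached | 18 minus that mean | Averaged over all trials |
|---|---|---|---|---|
| 20% | 24.2% | 14.4 | 3.6 | 1.0 |
| 25% | 42.6% | 13.8 | 4.2 | 2.0 |
| 30% | 61.1% | 13.1 | 4.9 | 3.2 |

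**3. Effect of acting at the fifth event.** Five events have occurred by patient 18 exactly when the fifth event occurs at or before patient 18. The sum of step 2 over k = 5 to 18 is 0.284, 0.481 and 0.667 at 20%, 25% and 30%, identical to step 1. Curtailment changes when the trial stops, not whether it does.

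**4. Enrolment while patient 18 is observed.** First dose to last dose is 9 weeks (63 days). Adding 90 days gives 153 days, which is 21.9 weeks or about 5.0 months. At 1-2 per month that is 5-10 more patients, out of 32 - 18 = 14 remaining. If the look came 10 weeks (about 2.3 months) after patient 18's first dose, it would be about 2-5.

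**The case against.** The strongest reply is that section 7.4 does not stand alone. Section 10.4 requires continuing safety evaluation and review at least monthly, and allows early termination. The trial is open-label at a single centre, so a fifth severe event would probably be noticed. This stands in part. A reader might infer that a doubling of toxicity would be stopped only 28-67% of the time. The documents do not support that: the figures describe the formal rule alone. But section 10.4 contains no threshold, so it does not commit anyone to act at the fifth event.

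A reader might also blame the low stopping probabilities on the single look. They come from the 5-of-18 cut-off, and step 3 shows that curtailment leaves them unchanged. It is also fair to say that 30% is the plan's declared null and that Table 2 gives 15% severe-to-fatal immune reactions for ipilimumab 3 mg/kg alone, which doubles to 30%. On that view 66.7% is the main figure. Still, doubling the lower end of the plan's own range gives 20%.

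The number of patients enrolled late can be overstated. Values up to about 8 arise only at 40-50% toxicity, which section 7.4 does not consider. Delayed recognition of events would also shrink the saving among the first 18.

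The overrun of 5-10 is likewise an upper case. Section 7.4 does not say that the full 90 days govern the look, and section 1.5.2 reports that immune-related events commonly begin 3 to 10 weeks after first dose.

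Lastly, the sentence on five or more events has no time point or denominator, so it could be read as a cap over all 32 patients. That fits poorly with the complementary 14-of-18 branch. It would also stop 21% of trials at 10% toxicity and 54% at 15%.

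**Conclusion.** The point holds as a gap in the timing of the rule. On its natural reading, section 7.4 lets accrual continue after its own answer is fixed. At 20-30% toxicity this happens in 24-61% of trials. When the boundary is reached, about 4 to 5 of the first 18 patients on average enrol after the fifth event. That average is an upper figure, because it assumes immediate knowledge of events in enrolment order.

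The detection figures are a separate, supporting observation. The formal rule is lenient at the plan's own null, continuing 33.3% of the time, and the plan does not disclose this. The documents do not show that the trial lacks other safety oversight, or that a fifth event would in practice be ignored.

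**What to change.** In section 7.4, state that accrual stops as soon as a fifth patient among the first 18 has a qualifying severe immune toxicity. This keeps the sponsor's boundary, decision and error rates. It concerns accrual only and does not address the management of patients already enrolled.

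Beside the rule, print its stopping probabilities: 2.8%, 12.1%, 28.4% and 66.7% at 10%, 15%, 20% and 30% toxicity. Say that section 10.4 review operates in addition. Define when patient 18 counts as assessed, and attach the denominator of 18 to the sentence on five or more events.

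The cost is a few sentences in an amendment. The one loss is efficacy, toxicity and correlative data from the patients not enrolled in trials that stop early. That is small, since those trials would have been declared too toxic anyway.
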